The primary analysis method for treatment comparisons of categorical efficacy and health outcomes variables at specific time points will be made using a logistic regression analysis with treatment, geographic region, and screening MRI/CRP status in the model. The odds ratio and 95% confidence intervals (CIs) will be reported. Treatment difference and 95% CI will also be reported. Secondary analysis will be conducted using a Fisher's exact test.

As a secondary analysis for the primary and major secondary categorical efficacy measures, a categorical mixed-effects model of repeated measures (categorical MMRM) estimating the percentage of patients achieving response across postbaseline visits may be used. The model will include treatment, geographic region, screening MRI/CRP status, visit, treatment-by-visit as fixed factors, as well as the continuous, fixed covariate of baseline value and baseline value-by-visit interaction (when appropriate). The binomial distribution and the logit link will be used. An unstructured covariance matrix will be used to model the within-patient variance-covariance errors. The Kenward-Roger approximation will be used to estimate the denominator degrees of freedom. The Newton-Raphson with ridging optimization technique will be used to aid with convergence. The probability of response, the corresponding 2-sided 95% CI, and the p-value for treatment comparisons at Week 16 (Visit 8), Week 52 (Visit 15), and all other postbaseline visits will be reported.

If the unstructured covariance matrix results in a lack of convergence, the heterogeneous Toeplitz covariance structure, followed by the heterogeneous autoregressive covariance structure, followed by the compound symmetry will be used. This order is specified according to a decreasing number of covariance parameters in the structure. The sandwich estimator (Diggle et al. 1994) for the covariance estimation will be used by specifying the EMPIRICAL option in SAS PROC MIXED. When sandwich estimation is used, the Kenward-Roger approximation for denominator degrees of freedom cannot be used. Instead, DDFM=BETWITHIN option will be used to estimate denominator degrees of freedom.

The primary analyses for continuous efficacy and health outcomes variables will be made using MMRM. A secondary analysis for continuous efficacy and health outcomes variables will be made using analysis of covariance (ANCOVA).

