## 5.2. Determination of Sample Size

Approximately 300 patients will be randomized at a 1:1:1 ratio in the Blinded Treatment Dosing Period (Period 2) to ixekizumab 80 mg Q2W, ixekizumab 80 mg Q4W, and placebo. With 100 patients per treatment group, this study will have approximately 98% power to test the superiority of ixekizumab Q2W to placebo for the ASAS40 at Week 16. The following assumptions were used for the power calculations for ASAS40 response rates at Week 16 regardless of starting dose: 46% for ixekizumab 80 mg Q2W treatment group and 18% for the placebo group. A 2-sided Fisher's exact test at the 0.05 level is assumed. These assumptions are based on the data from historical clinical studies in nonrad-axSpA patients with objective signs of inflammation (etanercept, adalimumab, certolizumab, and golimumab [Sieper et al. 2013; Dougados et al. 2014; Landewé et al. 2014; Sieper et al. 2015]).

There is little data from similarly designed 52-week placebo-controlled trials regarding the ASAS40 response rate for active and placebo treated patients to guide power estimation at Week 52. [Table RHBX.5.1](#) provides power estimates to test the superiority of ixekizumab Q2W to placebo for the ASAS40 at Week 52, assuming various ASAS40 response rates for ixekizumab Q2W and placebo at Week 52. A 2-sided Fisher's exact test at the 0.05 level is assumed.

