The primary analyses for continuous efficacy and health outcomes variables will be made using MMRM. The primary analyses for MRI endpoints will be made using analysis of covariance (ANCOVA). A secondary analysis for continuous efficacy and health outcomes variables will be made using ANCOVA.

When the MMRM is used, the model will include treatment, geographic region, screening MRI/CRP status, baseline value, visit, baseline value-by-visit, and treatment-by-visit interaction as fixed factors (except for the analysis of CRP, see paragraph below). The covariance structure to model the within-patient errors will be unstructured. The REML will be used. The Kenward-Roger method will be used to estimate the denominator degrees of freedom. Type III tests for the least-squares (LS) means will be used for the statistical comparison; the 95% CI will also be reported. Treatment group comparisons with placebo at Week 16 (Visit 8), Week 52 (Visit 15) and all other visits will be reported. If the unstructured covariance matrix results in a lack of convergence, the similar approach specified above for categorical MMRM will be used.

For the analysis of mean change from baseline and ratio of postbaseline to baseline in CRP, MMRM model will include treatment, geographic region, screening MRI/CRP status, visit, and treatment-by-visit interaction as fixed factors. Note for the ratio of postbaseline to baseline in CRP, analysis will be performed on the natural log transformed ratio.

When the ANCOVA is used, the model will include treatment, geographic region, screening MRI/CRP status, and baseline value (except for the analysis of CRP, see paragraph below).

Type III sums of squares for the Least Squares (LS) means will be used for the statistical comparison; the 95% CI will also be reported.

For the analysis of mean change from baseline and ratio of postbaseline to baseline in CRP, ANCOVA model will include treatment, geographic region and screening MRI/CRP status. Note for the ratio of postbaseline to baseline in CRP, analysis will be performed on the natural log transformed ratio.

For the analysis of ASDAS disease activity states (ie, inactive, low, high, and very high disease states), the repeated measures proportional odds model will include treatment, geographic region, screening MRI/CRP status, visit, and treatment-by-visit interaction.

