**Table RHBX.6.3. Geographic Regions for Statistical Analysis**

Geographic Region	Countries
Europe	Austria, Russia a , Czech Republic, Finland, Poland, Germany, Romania, The Netherlands
non-Europe	United States, Canada, Argentina, Brazil, Mexico, Japan, Korea

a Russia is combined with European countries due to the preponderance of investigative sites in the western part of Russia.

In general, when an MMRM is to be used for analyses, baseline value and baseline-by-visit interactions will be included as covariates; when an ANCOVA is to be used for analyses, baseline value will be included as a covariate.

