- Inflammatory back pain: n (%)
- Current and/or history of extra-axial involvement separately for: n (%)
  - anterior uveitis
  - psoriasis
  - inflammatory bowel disease (including Crohn's disease or ulcerative colitis)
  - dactylitis
  - arthritis
  - enthesitis.

Baseline C-Reactive Protein (CRP) level:

- CRP (mg/L)
- CRP categories: n (%)
  - $\leq 3.00$  mg/L,  $> 3.00$  mg/L
  - $\leq 5.00$  mg/L,  $> 5.00$  mg/L
  - $\leq 10.00$  mg/L,  $> 10$  mg/L
  - $\leq 15.00$  mg/L,  $> 15.00$  mg/L.

Baseline disease activity level, pain, function, and mobility:

- Ankylosing Spondylitis Disease Activity Score (ASDAS), ASDAS  $< 2.1$  or ASDAS  $\geq 2.1$ , and ASDAS  $\leq 3.5$  or ASDAS  $> 3.5$
- Bath Ankylosing Spondylitis Disease Activity Index (BASDAI), and  $4 \leq$  BASDAI  $< 6$  or BASDAI  $\geq 6$
- Patient global assessment of disease activity (numeric rating scale [NRS])
- Inflammation (mean of questions 5 and 6 of BASDAI)
- Individual BASDAI items (question 1-6) : fatigue, spinal pain, peripheral arthritis, enthesitis, intensity of morning stiffness and duration of morning stiffness
- Pain, NRS: spinal pain at night due to AS
- Pain, NRS: spinal pain due to AS
- Bath Ankylosing Spondylitis Functional Index (BASFI)
- Bath Ankylosing Spondylitis Metrology Index–Spinal Mobility (BASMI Linear)
- Chest expansion (in cm)
- Occiput-to-wall measurement (in cm).

Baseline peripheral arthritis and enthesitis:

- Tender Joint Count (TJC) based on 46 joints
  - TJC: mean (SD)
  - patients with  $> 0$  tender joint: n (%)
- Swollen Joint Count (SJC) based on 44 joints
  - SJC: mean (SD)
  - patients with  $> 0$  swollen joint: n (%)
- Maastricht Ankylosing Spondylitis Enthesitis Score (MASES)
  - MASES: mean (SD)
  - patients with MASES  $> 0$ : n (%)
- Spondyloarthritis Research Consortium of Canada (SPARCC) Enthesitis score
  - SPARCC: mean (SD)
  - patients with SPARCC score  $> 0$ : n (%).

Baseline health outcomes measures:

- Assessment of Spondyloarthritis International Society Health Index (ASAS HI), ASAS HI baseline  $\geq 3$ , and ASAS HI baseline  $> 5$
- Fatigue Severity NRS

- Jenkins Sleep Evaluation Questionnaire (JSEQ)
- European Quality of Life–5 Dimensions–5 Level (EQ-5D-5L) (EuroQol Group 2011)
- Work Productivity and Activity Impairment Questionnaire–Spondyloarthritis (WPAI-SpA)
- Short Form (36 items) Health Survey – SF36 Physical Component Summary (PCS) and Mental Component Summary (MCS) scores

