### **6.10.1. Primary Outcome and Methodology**

The primary outcomes are the proportion of patients achieving ASAS40 at Week 16 (Visit 8) for regulatory agencies that accept Week 16 as primary endpoint, and ASAS40 at Week 52 (Visit 15) for regulatory agencies that require Week 52 as primary endpoint. These are de-facto (effectiveness) estimands (that is, the effect attributable to the originally randomized treatment, ixekizumab 80 mg Q2W, ixekizumab 80 mg Q4W, and placebo, at the primary time points of Week 16 and Week 52 in all randomized patients). For inadequate responders who were treated with biologic rescue of ixekizumab 80 mg Q2W, only data up to the time of initiation of biologic rescue of ixekizumab 80 mg Q2W will be included in the primary analysis. These patients will be considered nonresponders to categorical assessment per the NRI imputation method after initiation of biologic rescue with ixekizumab 80 mg Q2W.

The primary analysis will be based on the ITT Population for Period 2 comparing each ixekizumab treatment group and placebo at Week 16 (Visit 8) and at Week 52 (Visit 15). The primary analysis is a logistic regression analysis with treatment, geographic region, and screening MRI/CRP status in the model (Section 6.1.2).

In the primary analysis, treatment groups of ixekizumab 80 mg Q2W and Q4W will be analyzed without regard to starting dose. The primary comparison will be tested based on the graphical multiple testing procedures detailed in Section 6.5.

[Table RHBX.6.5](#) provides the detailed analyses including analysis type, method and imputation, population, time point, and treatment comparisons for primary outcome.

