### **6.10.2. Major Secondary Efficacy Analyses**

The major secondary outcomes at Week 16 (Visit 8) are:

- Proportion of patients achieving ASAS40 response at Week 16 (for regulatory agencies that require Week 52 as primary endpoint)
- Change from baseline in ASDAS at Week 16
- Change from baseline in SF-36 PCS at Week 16
- Proportion of patients achieving ASDAS low disease activity (<2.1) at Week 16
- Change from baseline in BASDAI at Week 16
- Change from baseline in MRI of the SIJ [SPARCC score] at Week 16

The major secondary outcomes at Week 52 (Visit 15) are:

- Change from baseline in ASDAS at Week 52
- Change from baseline in SF-36 PCS at Week 52
- Proportion of patients achieving ASDAS low disease activity (<2.1) at Week 52
- Change from baseline in BASDAI at Week 52

The major secondary analysis will be based on the ITT Population for Period 2 comparing each ixekizumab treatment group and placebo at Week 16 and/or Week 52 as appropriate. In the major secondary analyses, treatment groups of ixekizumab 80 mg Q2W and Q4W will be analyzed without regard to starting dose.

The primary analysis for categorical major secondary outcomes is a logistic regression analysis with treatment, geographic region, and screening MRI/CRP status in the model (Section 6.1.2). For inadequate responders who were treated with biologic rescue of ixekizumab 80 mg Q2W, only data up to the time of initiation of biologic rescue of ixekizumab 80 mg Q2W will be included in the primary analysis. These patients will be considered nonresponders to categorical assessment per the NRI imputation method (Section 6.3.1) after initiation of biologic rescue with ixekizumab 80 mg Q2W.

The primary analysis for continuous major secondary outcomes (except MRI of SIJ SPARCC score) is an MMRM analysis with treatment, geographic region, screening MRI/CRP status, baseline value, visit, baseline value-by-visit, and treatment-by-visit interaction as fixed factors (Section 6.1.2). Data after initiation of biologic rescue of ixekizumab 80 mg Q2W will not be included in MMRM analyses.

The primary analysis for change from baseline in MRI of SIJ SPARCC score at Week 16 is an observed case analysis using ANCOVA with treatment, geographic region, screening MRI/CRP status and baseline value in the model (Section 6.1.2). Only patients with both baseline and Week 16 MRI of SIJ SPARCC score will be included in the analysis.

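### The confirmatory logistic model for ASDAS <2.1 leaves out baseline ASDAS, giving up a modest amount of power at almost no saving

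*SAP*

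**What the plan says.** For the primary endpoint, ASAS40, SAP 6.10.1 states: "The primary analysis is a logistic regression analysis with treatment, geographic region, and screening MRI/CRP status in the model". SAP 6.10.2 sets the model for ASDAS <2.1: "The primary analysis for categorical major secondary outcomes is a logistic regression analysis with treatment, geographic region, and screening MRI/CRP status in the model". SAP 6.1.2.1 and 6.5 describe the same model, and protocol 9.2.1 agrees with it. Missing responses are handled by nonresponder imputation (NRI).

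The continuous endpoints are treated differently. For the MMRM, "the model will include treatment, geographic region, screening MRI/CRP status, baseline value, visit, baseline value-by-visit, and treatment-by-visit interaction as fixed factors" (SAP 6.1.2.1). Section 6.2 adds that "when an ANCOVA is to be used for analyses, baseline value will be included as a covariate". The stated exception is CRP ("except for the analysis of CRP, see paragraph below"), which is not a major secondary endpoint. The section 6.2 covariate rule on baseline values is silent on logistic models.

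Table RHBX.6.4 defines the endpoint as a value of ASDAS below 2.1. The population column of Table RHBX.6.5 limits its main analysis to patients with baseline ASDAS of at least 2.1, although that row's analysis-type column and section 6.10.2 refer to the ITT population. Baseline ASDAS is already derived and summarised in section 6.7.1, under "Baseline disease activity level, pain, function, and mobility". Section 6.1.2.1 promises a treatment difference with a 95% CI beside the odds ratio, but does not say how it is computed.

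**The concern.** Whether a patient falls below a fixed threshold depends on where that patient starts. A baseline of 2.3 and a baseline of 4.5 face very different hurdles. Limiting the set to baseline values of at least 2.1 removes patients already below the line but leaves the variation above it. The SAP adjusts change in ASDAS for baseline ASDAS, then analyses a dichotomy of the same score without it.

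In a randomised comparison, omitting a prognostic covariate does not bias the test, but it makes the test less sensitive. ASDAS <2.1 sits in the confirmatory family, where alpha is divided. In the Week 16 list ASAS40 starts at 0.02 for Q2W and 0.03 for Q4W. In the Week 52 list 0.02 and 0.03 pass to the first tier of secondary endpoints. A test run at a fraction of 0.05 has less power to spare.

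**Working it through.** **1. The plan's own figure.** Inputs from SAP 5.2: 46% v 18%, 100 per arm; "A 2-sided Fisher's exact test at the 0.05 level is assumed". Exact enumeration of Fisher's test gives 98.8%, against the stated 98%. The weakest Week 52 case, 30% v 15%, gives 66.9% against 66%. Both are reproduced. They concern ASAS40; the documents give no power statement for ASDAS <2.1.

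**2. Assumed inputs for ASDAS <2.1.**
- Response 33% v 15%: assumption.
- 100 per arm: the planned size, before any restriction on baseline ASDAS.
- Alpha 0.02, two-sided: assumption, taken from the Q2W starting level. The level actually reaching this endpoint depends on within-tier weights in figures not available here.
- Baseline/follow-up correlation 0.2 to 0.6: assumption.
- Correlation of 0.6 between the CRP stratum and baseline ASDAS: assumption.

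**3. Hand check of the unadjusted power.** Pooled-variance formula: power = Φ[(Δ − z·SE0)/SE1].
- Δ = 0.33 − 0.15 = 0.18; mean rate 0.24; z = 2.326.
- SE0 = √(2 × 0.24 × 0.76/100) = 0.0604.
- SE1 = √((0.33 × 0.67 + 0.15 × 0.85)/100) = 0.0590.
- (0.18 − 2.326 × 0.0604)/0.0590 = 0.67, so power is about 75%.

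**4. Simulation with and without baseline ASDAS.** There were 4,000 trials per cell. Baseline was truncated at the threshold, the CRP stratum was in both models, and treatment was judged by a Wald test.

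| Correlation | Alpha 0.02: without → with | Gain | Alpha 0.01: without → with | Gain |
|---|---|---|---|---|
| 0.3 | 74.4 → 75.9 | 1.5 | 65.2 → 67.6 | 2.4 |
| 0.4 | 74.9 → 77.7 | 2.8 | 65.9 → 69.5 | 3.6 |
| 0.5 | 76.4 → 80.2 | 3.8 | 68.4 → 73.7 | 5.3 |
| 0.6 | 75.6 → 83.0 | 7.4 | 67.0 → 75.0 | 8.0 |

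At correlation 0.2 the gain is 0.5 point or less. The standard error of one cell is about √(0.75 × 0.25/4000) = 0.7 point. The column without baseline agrees with step 3. Type I error at nominal 5% was 4.8% without baseline and 5.0% with it.

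A separate simulation that also made 15% of patients random NRI failures (assumed) gave gains of about 2, 4 and 7 points at correlations 0.3, 0.5 and 0.6.

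**5. ASAS40 for comparison.** This used 46% v 18%, 100 per arm, 6,000 trials per cell. The prognostic strength was assumed: odds ratio per SD of 1.28, 1.65, 2.12 and 2.72, with 4.48 as an extreme.
- Alpha 0.02: 97.7 → 97.9, 97.4 → 97.9, 97.6 → 98.7, 97.4 → 99.0; extreme 97.5 → 99.5.
- Alpha 0.05: every gain is below 1 point.
- Week 52 at 30% v 15%, alpha 0.05: 72.8 → 73.0, 71.4 → 73.1, 71.9 → 75.5, 72.1 → 77.8; extreme 72.4 → 83.1.

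**The case against.** The strongest reply is that the plan follows a recognised rule: adjust for the stratification factors, with country grouped into region. Protocol and SAP agree on that model. Screening CRP status, a coarse marker of one ASDAS component, is already in it, and the restriction to baseline ASDAS of at least 2.1 narrows the range. The rates, the correlation and the alpha used above are all assumptions.

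Much of this stands. The stratum and NRI do take part of the gain: a simulation that ignores them gives 4, 6 and 10 points, where those allowing for the stratum give about 2, 4 and 7. But the gain does not vanish, and following the stratification rule does not explain why change in ASDAS is baseline-adjusted and its dichotomy is not.

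A reader might infer three stronger things that the documents do not support.
- *The primary ASAS40 analysis has the same fault.* ASAS40 is already defined by percent and absolute change from baseline, and nothing in the documents shows that baseline ASDAS predicts it. At the planned Week 16 rates there is almost no power left to recover. The larger Week 52 gains need both a small effect and a strongly predictive score.
- *The SAP removed a covariate from the confirmatory model.* It did not. Only the optional, secondary categorical MMRM in protocol 9.2.1 allowed a baseline value, where appropriate. The SAP version of that secondary model leaves it out.
- *Every continuous endpoint is adjusted for baseline.* The CRP models are not. The contrast holds for the continuous major secondary endpoints.

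**Conclusion.** The point holds for ASDAS <2.1 at Weeks 16 and 52, as lost efficiency. It is not an error, a bias or a threat to type I error. A plausible gain is about 2 to 7 points of power for correlations between 0.3 and 0.6, and close to nothing at 0.2. That size rests on 33% v 15%, 100 per arm and alpha 0.02, none of which the documents give for this endpoint. The direction is firmer than the size, because the endpoint is a threshold on the covariate's own scale. For ASAS40 no material gain is shown at the plan's Week 16 rates, and adjustment there is optional.

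**What to change.** Before unblinding, amend SAP 6.1.2.1, 6.10.2 and Table RHBX.6.5 as follows.

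1. Add baseline ASDAS as a continuous covariate to the logistic model for ASDAS <2.1 at Weeks 16 and 52.
2. Obtain the treatment difference and its CI by standardising the fitted model over the analysis population. This also settles how that difference is computed.
3. State a rule for a missing baseline ASDAS, since the score is missing if any component is missing and the patient would otherwise drop out of the model. For example, use the screening value (the schedule of activities collects the components at screening) or else the overall mean.
4. Make Table RHBX.6.5 and section 6.10.2 agree on the analysis set, so that steps 2 and 3 apply to a defined population.

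The cost is a few lines of SAP text and no new data. The odds ratio becomes conditional on one more covariate; it is already conditional on region and stratum, and the standardised difference gives a marginal effect beside it. Protocol 9.2.1 states the logistic model without this term. Under protocol 9.2 the change and its justification would therefore be described in the study report, unless the sponsor regards it as a principal feature that needs an amendment.

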### **6.10.2. Major Secondary Efficacy Analyses**

The major secondary outcomes at Week 16 (Visit 8) are:

- Proportion of patients achieving ASAS40 response at Week 16 (for regulatory agencies that require Week 52 as primary endpoint)
- Change from baseline in ASDAS at Week 16
- Change from baseline in SF-36 PCS at Week 16
- Proportion of patients achieving ASDAS low disease activity (<2.1) at Week 16
- Change from baseline in BASDAI at Week 16
- Change from baseline in MRI of the SIJ [SPARCC score] at Week 16

The major secondary outcomes at Week 52 (Visit 15) are:

- Change from baseline in ASDAS at Week 52
- Change from baseline in SF-36 PCS at Week 52
- Proportion of patients achieving ASDAS low disease activity (<2.1) at Week 52
- Change from baseline in BASDAI at Week 52

The major secondary analysis will be based on the ITT Population for Period 2 comparing each ixekizumab treatment group and placebo at Week 16 and/or Week 52 as appropriate. In the major secondary analyses, treatment groups of ixekizumab 80 mg Q2W and Q4W will be analyzed without regard to starting dose.

The primary analysis for categorical major secondary outcomes is a logistic regression analysis with treatment, geographic region, and screening MRI/CRP status in the model (Section 6.1.2). For inadequate responders who were treated with biologic rescue of ixekizumab 80 mg Q2W, only data up to the time of initiation of biologic rescue of ixekizumab 80 mg Q2W will be included in the primary analysis. These patients will be considered nonresponders to categorical assessment per the NRI imputation method (Section 6.3.1) after initiation of biologic rescue with ixekizumab 80 mg Q2W.

The primary analysis for continuous major secondary outcomes (except MRI of SIJ SPARCC score) is an MMRM analysis with treatment, geographic region, screening MRI/CRP status, baseline value, visit, baseline value-by-visit, and treatment-by-visit interaction as fixed factors (Section 6.1.2). Data after initiation of biologic rescue of ixekizumab 80 mg Q2W will not be included in MMRM analyses.

The primary analysis for change from baseline in MRI of SIJ SPARCC score at Week 16 is an observed case analysis using ANCOVA with treatment, geographic region, screening MRI/CRP status and baseline value in the model (Section 6.1.2). Only patients with both baseline and Week 16 MRI of SIJ SPARCC score will be included in the analysis.

These major secondary comparisons will be tested based on the graphical multiple testing procedure detailed in Section 6.5.

Table RHBX.6.5 provides the detailed analyses including analysis type, method and imputation, population, time point, and treatment comparisons for major secondary outcomes.

